6.9. Appendix 9 Laboratory Toxicity Grading

The laboratory abnormalities will be determined according to the criteria specified in the DAIDS Toxicity Grading Scale (see Clinical Protocol Appendix 8, DAIDS Table) or in accordance with the normal ranges of the clinical laboratory if no gradings are available.

ATTACHMENT 1. SIMULATIONS FOR SAMPLE SIZE JUSTIFICATION

We conducted a simulation study to assess the expected precision in our estimates of the primary efficacy endpoint if we achieve the target sample size of 24 participants across Panels 1 and 2, and further how the precision would decrease with only 20 or 16 participants.

Assumptions of the Data-Generating Model

We simulated data according to the binomial mixed model as specified in Sections 5.3.1.2.2.1 and 5.3.1.2.2.2. We used the logit model specified in Section 5.3.1.2.2.2 to allow for between-panel differences in the intercept (baseline estimate) and slope (change from baseline):

$$\text{logit}(p_{ij}) = \underbrace{[\alpha + \delta_\alpha I(\text{panel}_i = 1) + \xi_i]}_{\text{intercept}} + \underbrace{[\beta + \delta_\beta I(\text{panel}_i = 1) + \gamma_i] j}_{\text{slope}}$$

where p_{ij} is the probability of a hepatocyte being HBsAg+ for subject i at visit j .

Datasets were simulated with either 16, 20, or 24 subjects (split between two equal-sized panels), and where we varied two aspects of the data:

- The true proportions of HBsAg+ hepatocytes for each panel at each time point. These are specified indirectly by setting the values of α , δ_α , β , and δ_β . See Table 10 for the list of scenarios. Generally, the true proportions at baseline were assumed to be higher in Panel 1 than in Panel 2 because Panel 1 subjects are untreated at baseline.
- The true inter-subject variability of the slope, SD_{slope} , where $\gamma_i \sim N(0, SD_{\text{slope}})$. For each scenario listed in 10, we examined the effect of setting SD_{slope} to 0.5, 1.0, or 2.0.

Table 10: List of scenarios for assumptions on the true proportion of HBsAg+ hepatocytes for each panel at each time point

Scenario ID	Group	% HBsAg+ hepatocytes		Reduction from baseline		Between-panel (1-2) difference in reduction from baseline	
		Baseline	Week 40	Absolute	Relative	Absolute	Relative
A	Panel 1	75%	5%	70%	93.3%	41%	-3.3%
	Panel 2	30%	1%	29%	96.7%		
	Overall	52.5%	3%	49.5%	94.3%		
B	Panel 1	75%	5%	70%	93.3%	50%	26.7%
	Panel 2	30%	10%	20%	66.7%		
	Overall	52.5%	7.5%	45%	85.7%		
C	Panel 1	60%	20%	40%	66.7%	20%	0%
	Panel 2	30%	10%	20%	66.7%		
	Overall	45%	15%	30%	66.7%		

Within each scenario, we set the percent of HBsAg+ hepatocytes at baseline and Week 40 for both Panels 1 and 2. From these four numbers (highlighted in **bold**), the remaining numbers in the table are derived. Data were simulated for each scenario using various sample sizes (assuming an equal number of subjects in each panel) and various values of SD_{slope} (standard deviation for the inter-subject random slope).

The true inter-subject variability of the intercept, $SD_{\text{intercept}}$, where $\xi_i \sim N(0, SD_{\text{intercept}})$, was set to 1.0 across all simulations based on the inter-subject differences observed from the donors data.

In contrast, inter-subject differences in the slopes are unknown, so a range of values of SD_{slope} were considered.

The number of HBsAg⁺ hepatocytes for subject i at visit j , denoted Y_{ij} , was simulated as $Y_{ij} \sim \text{Binomial}(N_{ij}, p_{ij})$, where N_{ij} is the total number of hepatocytes sampled during a biopsy. Based on the donors data, we simulated $\log(N_{i0}) \sim N(10, 0.35)$ for the baseline biopsy, and then $\log(N_{i1}) \sim N(\log(N_{i0}), 0.1)$ for the Week 40 biopsy; values of N_{i0} and N_{i1} were then rounded to integers.

Statistical Analysis of the Simulated Data

For each simulated dataset, we fit both the overall model as specified in Section 5.3.1.2.2.1 and the between-panel model as specified in Section 5.3.1.2.2.2. From the overall model, we estimated the absolute and relative reductions from baseline in the overall proportion of HBsAg⁺ hepatocytes. From the between-panel model, we estimated the between-panel differences in the reductions. For each estimate we obtained an 80% confidence interval (CI). Note that, for ease of interpretation, we present the changes from baseline as “reductions” – simply the negative of changes – so that most of the reported numbers are positive. I.e., a change from 75% to 5% is reported as an absolute reduction of 70% rather than as an absolute change of -70%.

We averaged all the estimates across 1000 simulations. The primary metric of interest is the width of the 80% CIs, which tell us how precisely we can estimate the reductions of interest given the sample size and the assumptions of the data-generating model.

Simulation Results

The 80% CI widths are presented in Figure 3 and again, together with point estimates and 80% CI limits, in Table 11. Generally, we see little bias in the point estimates – the average estimated reductions and differences in reductions in Table 11 match well with the scenario assumptions in 10. This is as expected, as binomial mixed models were used to both simulate the data and carry out the estimation.

The precision of the estimates are of course greater – meaning narrower CIs – with 12 patients per panel than with either 8 or 10 patients. However, the loss in precision with fewer patients is not large in the simulated scenarios, as shown in Figure 3. E.g., in Scenario A with $SD_{slope} = 1.0$, as the sample size per panel increases from 8 to 12 the width of the 80% CI decreases from 20.3% to 16.7% for the overall absolute reduction from baseline; and from 21.8% to 18.1% for the between-panel difference in the absolute reduction.

For the overall absolute reduction (OAR) from baseline, varying the value of SD_{slope} has minimal impact on the CI widths. Across Scenarios A, B, and C, the CI widths vary from roughly 8% to 17% with 12 patients per panel and from 10% to 21% with 8 patients per panel. Generally, the CI widths appear to be larger when the true OAR is larger.

For the overall relative reduction (ORR) from baseline, both the value of SD_{slope} and the scenario assumptions (A, B, or C) have large impacts on the CI widths. In Scenario A the precision was

[figure not shown]
excellent regardless of the value of SD_{slope} , but in Scenario C the precision is both worse and highly dependent on the value of SD_{slope} . In contrast with the OAR, the CI widths for the estimated ORR appear to be larger when the true ORR is smaller.

The general pattern of CI widths observed for the OAR and ORR hold as well for the between-panel difference in absolute reduction (DAR) and relative reduction (DRR). That this, the CI widths for the DAR do not vary much by SD_{slope} , but are larger when the within-panel absolute reductions (which the model must estimate for each panel in order to estimate the between-panel DAR) are larger. For the DRR, the CI widths vary both by SD_{slope} and scenario, with larger widths when the within-panel relative reductions are smaller. The CI widths for the DAR and DRR are of course larger than for the OAR and ORR – the model for between-panel differences has more parameters to estimate and, from another perspective, the DAR is essentially the difference between two OARs, and so the imprecision of the two OARs combine and propagate to the DAR (and analogously for the DRR as the difference of two ORRs).

Conclusions and Recommendations

The gains in precision as the sample size per panel increases from 8 to 12 are not large – the bigger factors are the true effect sizes and the between-patient variability, both of which are beyond our control. Yet we recommend maintaining the current target of 12 patients per panel (for Panels 1 and 2) both to gain as much precision as is feasible and to allow for the likelihood of incomplete data due to patient dropout. Assuming 20% dropout, we would have only 9-10 patients per panel with usable data for the primary analysis. With this sample size, we may still achieve adequate precision for the overall reduction from baseline, whether absolute or relative. For the between-panel differences, however, we have less confidence in achieving adequate precision regardless of the sample size we choose.

Figure 3: Simulation-based estimated widths of 80% confidence intervals for the (i and ii) overall and (iii and iv) between-panel analyses of the reduction in proportion of positive hepatocytes

The widths of the 80% CIs were obtained by averaging the estimates across 1000 simulations. The true proportions of HBsAg+ hepatocytes at baseline → Week 40 in each scenario were:

Scenario A: 75% → 5% for Panel 1 and 30% → 1% for Panel 2

Scenario B: 75% → 5% for Panel 1 and 30% → 10% for Panel 2

Scenario C: 60% → 20% for Panel 1 and 30% → 10% for Panel 2

Table 11: Simulation-based estimates for the overall and between-panel analyses of the reduction in proportion of positive hepatocytes

Scenario ID	SDslope	Sample size per panel	Overall reduction from baseline (80% CI) [width of 80% CI]		Between-panel (1-2) difference in reduction from baseline (80% CI) [width of 80% CI]	
			Absolute (%)	Relative (%)	Absolute (%)	Relative (%)
A	0.5	8	50.6 (40.5,60.8) [20.3]	95.7 (94.5,97.0) [2.4]	39.4 (28.8,50.0) [21.2]	-3.5 (-6.2,-0.8) [5.4]
		10	50.7 (41.8,59.7) [17.9]	95.7 (94.6,96.8) [2.2]	39.2 (29.6,48.9) [19.3]	-3.4 (-5.8,-1.0) [4.8]
		12	50.8 (42.5,59.1) [16.7]	95.7 (94.7,96.7) [2.0]	40.4 (31.5,49.2) [17.6]	-3.5 (-5.8,-1.3) [4.5]
	1.0	8	50.7 (40.6,60.8) [20.3]	95.6 (93.8,97.3) [3.5]	39.1 (28.2,50.0) [21.8]	-3.6 (-7.7,0.5) [8.3]
		10	50.4 (41.3,59.5) [18.2]	95.6 (94.1,97.2) [3.1]	39.3 (29.4,49.2) [19.8]	-3.5 (-7.1,0.2) [7.4]
		12	50.9 (42.5,59.3) [16.7]	95.7 (94.3,97.1) [2.8]	40.2 (31.1,49.2) [18.1]	-3.6 (-6.9,-0.3) [6.7]
	2.0	8	50.4 (40.2,60.6) [20.5]	95.1 (91.9,98.4) [6.5]	38.4 (26.1,50.7) [24.6]	-4.2 (-12.9,4.4) [17.3]
		10	50.3 (41.2,59.5) [18.4]	95.4 (92.6,98.1) [5.5]	39.6 (28.8,50.4) [21.6]	-3.7 (-10.8,3.5) [14.3]
		12	50.8 (42.5,59.2) [16.7]	95.5 (93.0,98.0) [4.9]	39.7 (29.9,49.6) [19.6]	-3.8 (-10.1,2.6) [12.7]
B	0.5	8	45.7 (36.9,54.5) [17.6]	86.4 (79.8,93.1) [13.3]	49.1 (40.7,57.4) [16.7]	27.0 (19.2,34.8) [15.5]
		10	45.7 (37.8,53.6) [15.8]	86.5 (80.5,92.4) [11.9]	49.8 (42.5,57.2) [14.8]	26.9 (19.9,34.0) [14.1]
		12	45.8 (38.6,52.9) [14.3]	86.5 (81.2,91.9) [10.7]	49.4 (42.5,56.3) [13.8]	27.0 (20.6,33.4) [12.8]
	1.0	8	45.6 (36.5,54.7) [18.1]	86.0 (78.3,93.7) [15.5]	49.4 (39.9,58.9) [19.0]	28.0 (13.3,42.7) [29.3]
		10	45.6 (37.5,53.7) [16.2]	86.3 (79.6,93.1) [13.5]	49.3 (40.8,57.9) [17.1]	27.6 (14.6,40.6) [26.0]
		12	45.7 (38.3,53.1) [14.8]	86.4 (80.3,92.5) [12.2]	49.6 (41.9,57.4) [15.5]	27.3 (15.6,39.1) [23.6]
	2.0	8	44.7 (34.5,55.0) [20.5]	85.1 (74.1,96.1) [22.0]	50.0 (36.1,63.9) [27.8]	31.7 (1.0,62.5) [61.5]
		10	45.2 (36.2,54.2) [18.0]	85.5 (76.0,95.0) [19.0]	49.5 (37.4,61.6) [24.2]	29.6 (3.1,56.1) [52.9]
		12	45.8 (37.6,53.9) [16.2]	85.9 (77.4,94.4) [17.0]	49.4 (38.4,60.4) [21.9]	28.9 (5.3,52.5) [47.2]
C	0.5	8	29.9 (24.8,35.1) [10.3]	67.6 (61.5,73.8) [12.3]	19.0 (11.4,26.7) [15.3]	0.1 (-11.0,11.1) [22.1]
		10	29.9 (25.3,34.6) [9.3]	67.6 (62.1,73.1) [11.1]	19.7 (12.9,26.5) [13.6]	-0.2 (-10.2,9.9) [20.1]
		12	30.0 (25.8,34.2) [8.4]	67.7 (62.7,72.8) [10.0]	19.5 (13.3,25.8) [12.5]	0.1 (-9.0,9.3) [18.3]
	1.0	8	29.7 (23.3,36.0) [12.7]	66.8 (56.8,76.8) [20.0]	19.0 (8.2,29.7) [21.5]	0.4 (-19.1,19.9) [39.0]
		10	29.9 (24.2,35.5) [11.3]	67.4 (58.5,76.2) [17.7]	19.1 (9.5,28.7) [19.2]	0.6 (-16.8,18.0) [34.8]
		12	29.9 (24.7,35.0) [10.3]	67.5 (59.4,75.5) [16.0]	19.4 (10.7,28.2) [17.5]	-0.3 (-16.1,15.5) [31.6]
	2.0	8	28.8 (19.1,38.6) [19.5]	65.3 (46.7,83.8) [37.1]	18.2 (-0.6,37.1) [37.7]	1.5 (-37.3,40.4) [77.8]
		10	29.4 (20.8,37.9) [17.1]	66.2 (49.9,82.5) [32.6]	19.1 (2.6,35.5) [32.9]	1.4 (-32.8,35.5) [68.3]
		12	29.7 (22.0,37.4) [15.4]	67.0 (52.3,81.7) [29.4]	19.3 (4.4,34.2) [29.8]	1.6 (-29.1,32.3) [61.4]

Each point estimate, along with the width of its 80% CI, was obtained by averaging the estimates across 1000 simulations. The true proportions of HBsAg+ hepatocytes at baseline → Week 40 in each scenario were:

Scenario A: 75% → 5% for Panel 1 and 30% → 1% for Panel 2

Scenario B: 75% → 5% for Panel 1 and 30% → 10% for Panel 2

Scenario C: 60% → 20% for Panel 1 and 30% → 10% for Panel 2

ATTACHMENT 2. SELECTED MAJOR PROTOCOL DEVIATIONS FOR ANALYSIS PURPOSES

The major protocol deviations that may affect the assessment of efficacy will be finalized prior to the primary analysis database lock. The major deviations that are selected to exclude participants from the PP set are listed below.

Sequence No.	Protocol Deviation Description (DVTERM)	Protocol Deviation Coded Term (DVDECOD)	Exclude from PP
1	Inclusion criterion 3 not met: Participant had not confirmed chronic HBV infection. In addition, chronicity was not documented at least 6 months prior to screening.	Entered but did not satisfy criteria	Yes
2	Inclusion criterion 4 not met: For Panel 1 Participant not currently treated including treatment naïve participants was not: a. HBeAg positive, AND b. with serum HBV DNA at screening \geq 20,000 IU/mL, AND c. with ALT levels at screening $<$ 10x ULN, AND d. with indication for NA treatment according to local standard practice	Entered but did not satisfy criteria	Yes
3	Inclusion criterion 4.1 not met: For Panel 3 Participant not currently treated was not: a. HBeAg positive AND with serum HBV DNA at screening \geq 20,000 IU/mL OR HBeAg negative AND with serum HBV DNA at screening \geq 2,000 IU/mL, AND b. with ALT levels at screening $<$ 10x ULN, AND c. with indication for NA treatment according to local standard practice	Entered but did not satisfy criteria	Yes
4	Inclusion criterion 5 not met: For Panel 2 Virologically suppressed participant was not: a. HBeAg negative b. on stable HBV treatment, defined as currently receiving NA treatment (ETV, tenofovir disoproxil, or TAF) for at least 6 months prior to screening and have been on the same NA treatment regimen (at the same dose) for at least 3 months at the time of screening, AND c. with serum HBV DNA $<$ 60 IU/mL on 2 measurements at least 3 months apart (one of which is at screening), AND d. with documented ALT values $<$ 2.0x ULN on 2 measurements at least 3 months apart (one of which is at screening).	Entered but did not satisfy criteria	Yes
5	Inclusion criterion 5.1 not met: For Panel 3 Patients HBeAg negative or HBeAg positive Virologically suppressed participant not a. on stable HBV treatment, defined as currently receiving NA treatment (ETV, tenofovir disoproxil, or TAF) for at least 6 months prior to screening and have been on the same NA treatment regimen (at the same dose) for at least 3 months at the time of screening, AND b. with serum HBV DNA $<$ 60 IU/mL on 2 measurements at least 3 months apart (one of which is at screening), AND c. with documented ALT values $<$ 2.0x ULN on 2 measurements at least 3 months apart (one of which is at screening).	Entered but did not satisfy criteria	Yes
6	Inclusion Criterion 6 not met: Participant has HBsAg \leq 100 IU/mL at screening.	Entered but did not satisfy criteria	Yes
7	Inclusion Criterion 8 not met: Participant did not have fibroscan liver stiffness measurement \leq 9.0 kPa within 6 months prior to screening or at the time of screening. Note: Other radiologic liver staging modalities (eg, acoustic radiation force impulse) might be used if standard practice at the site or if otherwise validated and agreed with the sponsor. Results should be equivalent to Metavir F0-F2 with absence of signs of portal hypertension.	Entered but did not satisfy criteria	Yes
8	Exclusion Criterion 1.2 met: Participant had evidence of hepatitis A virus (hepatitis A antibody IgM), HCV infection (HCV antibody), hepatitis D virus (HDV) infection (HDV antibody).	Entered but did not satisfy criteria	Yes

Sequence No.	Protocol Deviation Description (DVTERM)	Protocol Deviation Coded Term (DVDECOD)	Exclude from PP
	
or hepatitis E virus (HEV) infection (HEV antibody IgM), or HIV-1 or HIV-2 infection (confirmed by antibodies) at screening.
 
Note: Participants with a positive HCV antibody test can be enrolled if they have negative HCV RNA at screening and documented negative HCV RNA at least 6 months prior to screening.
 
Note: Participants with a positive HDV antibody test may be enrolled after discussion with the sponsor if an active HDV co-infection can be ruled out by documentation of negative HDV RNA.
 
Note: Participants with a positive IgM antibody test for HEV infection may be enrolled after discussion with the sponsor if an active HEV infection can be ruled out by documentation of negative anti-HEV IgG.
 
Note: Participants with a positive HIV-1 or HIV-2 antibody/antigen test at screening should have a confirmatory HIV RNA test, to rule out false positive results. They can be enrolled if they have a negative HIV RNA test at screening. Participants with evidence of HIV-1 or HIV-2 infection who are on antiretroviral treatment are excluded.
		
9	
Exclusion Criterion 2 met:
 
Participant had any of the following laboratory abnormalities within 12 months prior to screening or at the time of screening:
 
 Total bilirubin >1.5x ULN, OR Direct bilirubin >1.2x ULN, OR Serum albumin <3.2 g/dL 	Entered but did not satisfy criteria	Yes
10	
Exclusion Criterion 3 met:
 
Participant had history or evidence of clinical signs/symptoms of hepatic decompensation manifested through <enter signs/symptoms>
	Entered but did not satisfy criteria	Yes
11	
Exclusion Criterion 4 met:
 
Participant had evidence of liver disease of non-HBV etiology: <enter liver disease etiology>
	Entered but did not satisfy criteria	Yes
12	Subject used disallowed medication as specified in the concomitant medication protocol Section:<specify treatment, dose, unit, frequency, reason administered>.	Received a disallowed concomitant treatment	Yes if classified as major protocol deviation
13	Received wrong treatment of study drug JNJ-3989/JNJ6379: incorrect dose when randomized to active (and vice versa)	Received wrong treatment or incorrect dose	Yes if classified as major protocol deviation
14	Subject did not receive dose of study drug JNJ-3989 within window: Within three weeks of the planned administration JNJ-3989 should be administered, if realized later than three weeks the dose should be skipped and administration of the next planned dose as per visit schedule should be awaited.	Received wrong treatment or incorrect dose	Yes if classified as major protocol deviation
15	Subject missed NA treatment for more than 5 doses within a four week period.	Received wrong treatment or incorrect dose	Yes if classified as major protocol deviation
16	Subject received expired study medication <JNJ-3989, JNJ-6379, NA, PegIFN-a2a or placebo>.	Received wrong treatment or incorrect dose	Yes if classified as major protocol deviation
17	Subject has confirmed signs of hepatic decompensation <specify> but subject continued study treatment.	Developed withdrawal criteria but not withdrawn	Yes
18	The subject has confirmed HBV virological breakthrough but continued study treatment.	Developed withdrawal criteria but not withdrawn	Yes
19	Study procedure not done at scheduled Visits.	Other	Yes if classified as major protocol deviation
20	Efficacy evaluation not done at scheduled Visits	Other	Yes if classified as major protocol deviation
21	Study Visits not performed per protocol.	Other	Yes if classified as major protocol deviation

ATTACHMENT 3. SAS CODE TO FIT BINOMIAL MIXED MODELS

SAS (version 9.4) PROC NLMIXED may be used to fit the binomial mixed models specified in Sections 5.3.1.2.2.1 and 5.3.1.2.2.2. The advantage of NLMIXED over PROC GLIMMIX – which can also fit binomial mixed models – lies in the power of NLMIXED's ESTIMATE statement, which can conveniently estimate non-linear functions of model parameters. In particular, this allows for convenient estimation of both point estimates and confidence intervals for the absolute and relative changes from baseline and the between-panel differences in the changes.

For the overall analysis in Section 5.3.1.2.2.1, code similar to the following may be used, where the input dataset `insight` should have variables named `id`, `time`, `y`, and `N`.

```
%macro expit(x);
  (exp(&x) / (1 + exp(&x)))
%mend;

ods output AdditionalEstimates=estimates; * save ESTIMATE statement output;
proc nlmixed data=insight alpha=0.2;
  parms a b 0 SD_int SD_slope 0.5; * initialize parameters;

  * specify binomial model with random effects;
  intercept = a + RE_int;
  slope = b + RE_slope;
  logit_p = intercept + slope*time;
  p = %expit(logit_p);
  random RE_int RE_slope ~ normal([0,0],[SD_int**2,0,SD_slope**2]) subject=id;
  model y ~ binomial(N,p);

  * estimate proportions and the change in proportions;
  p0 = %expit(a);
  p1 = %expit(a+b);
  estimate "(1) p0" 100*p0;
  estimate "(2) p1" 100*p1;
  estimate "(3) Abs. change (p1-p0)" 100*(p1 - p0);
  estimate "(4) Rel. change (p1-p0)/p0" 100*(p1/p0 - 1);
run;
```

For the between-panel analysis in Section 5.3.1.2.2.2, code similar to the following may be used, where the input dataset `insight` should have variables named `id`, `time`, `panel`, `y`, and `N`.

```
ods output AdditionalEstimates=estimates; * save ESTIMATE statement output;
proc nlmixed data=insight alpha=0.2;
  parms a delta_a b delta_b 0 SD_int SD_slope 0.5; * initialize parameters;

  * specify binomial model with random effects;
  intercept = a + delta_a*(panel = 1) + RE_int;
  slope = b + delta_b*(panel = 1) + RE_slope;
  logit_p = intercept + slope*time;
  p = %expit(logit_p);
  random RE_int RE_slope ~ normal([0,0],[SD_int**2,0,SD_slope**2]) subject=id;
  model y ~ binomial(N,p);

  * estimate proportions, changes in proportions, and differences in changes;
  q0 = %expit(a);
  q1 = %expit(a+b);
```

```
p0 = %expit(a+delta_a);
p1 = %expit(a+delta_a + b+delta_b);

estimate "(A1) Panel 1: p0" 100*p0;
estimate "(A2) Panel 1: p1" 100*p1;
estimate "(A3) Panel 1: Abs. change (p1-p0)" 100*(p1 - p0);
estimate "(A4) Panel 1: Rel. change (p1-p0)/p0" 100*(p1/p0 - 1);

estimate "(B1) Panel 2: q0" 100*q0;
estimate "(B2) Panel 2: q1" 100*q1;
estimate "(B3) Panel 2: Abs. change (q1-q0)" 100*(q1 - q0);
estimate "(B4) Panel 2: Rel. change (q1-q0)/q0" 100*(q1/q0 - 1);

estimate "(C1) Panel 1 minus 2: Diff in abs. change (A3-B3)"
100*(p1 - p0) - 100*(q1 - q0);
estimate "(C2) Panel 1 minus 2: Diff in rel. change (A4-B4)"
100*(p1/p0 - 1) - 100*(q1/q0 - 1);

run;
```

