5.1.7. Level of Significance

Due to the exploratory nature of this study, no formal statistical test will be performed. Two-sided 80% CI will be provided with the summary statistics. No adjustment for multiple CIs will be made.

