Estimates of the absolute and relative changes from baseline in the proportion of HBsAg+ hepatocytes at Week 40 and associated 80% CIs will be obtained from the model as follows. Let p_0 and p_1 be the proportion of infected hepatocytes at times 0 (baseline) and 1 (Week 40) for a “typical” subject. Based on the binomial model, $p_0 = \text{expit}(\alpha)$ and $p_1 = \text{expit}(\alpha + \beta)$, where $\text{expit}(x) = \exp(x)/[1 + \exp(x)]$ is the inverse of the logit function. The absolute and relative changes from baseline are therefore

- Absolute change: $p_1 - p_0 = \text{expit}(\alpha + \beta) - \text{expit}(\alpha)$
- Relative change: $\frac{p_1 - p_0}{p_0} = \frac{p_1}{p_0} - 1 = \frac{\text{expit}(\alpha + \beta)}{\text{expit}(\alpha)} - 1$

SAS code to fit the binomial mixed model and estimate the quantities of interest is provided in [Attachment 3](#). We may also report estimates and CIs for p_0 and p_1 .

Additional models may be evaluated depending on the distribution of data (such as Poisson, Negative-Binomial or Zero-Inflated regression models) and comparison of fit statistics would be performed to select the most adequate model. Additional covariates may be added to the model based on clinical considerations.

All biopsy data will be used for this analysis, including data collected after treatment discontinuation or occurrence of major protocol deviations ([Appendix 4](#)) potentially affecting the primary endpoint (see [Attachment 2](#)).

5.3.1.2.2.2. Comparison Between Panels 1 and 2

Study panel will be included as an additional covariate in the model described in Section [5.3.1.2.2.1](#). That is, the model for $\text{logit}(p_{ij})$ will become

$$\text{logit}(p_{ij}) = \underbrace{[\alpha + \delta_\alpha I(\text{panel}_i = 1) + \xi_i]}_{\text{intercept}} + \underbrace{[\beta + \delta_\beta I(\text{panel}_i = 1) + \gamma_i] j}_{\text{slope}}$$

with:

- α : Fixed intercept for a “typical” Panel 2 subject
- δ_α : Fixed difference in intercepts (Panel 1 minus Panel 2) for “typical” subjects
- β : Fixed slope for a “typical” Panel 2 subject
- δ_β : Fixed difference in slopes (Panel 1 minus Panel 2) for “typical” subjects
- panel_i : Panel number (1 or 2) for subject i

All other aspects of the model are unchanged from the specification in Section [5.3.1.2.2.1](#).

The input data for this model are Y_{ij} , N_{ij} , panel_{*i*}, and *n*. There are six parameters to estimate: α , δ_α , β , δ_β , SD_{intercept}, and SD_{slope}.

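### Within-panel 80% intervals for relative change are symmetric on the raw percent scale: they miss more often by overstating the reduction, and at slope SD 2.0 with 8 to 10 evaluable per panel some pass 100%

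*SAP*

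**What the plan says.** SAP 5.3.1.2.2.1 plans "Estimates of the absolute and relative changes from baseline in the proportion of HBsAg+ hepatocytes at Week 40 and associated 80% CIs" from a binomial mixed model. SAP 5.3.1.2.2.2 extends this to each panel and to the between-panel difference. SAP 5.1.7 sets the level: "Two-sided 80% CI will be provided with the summary statistics".

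Attachment 3 supplies the code. It calls "proc nlmixed data=insight alpha=0.2" and chooses NLMIXED for its ESTIMATE statement, "which can conveniently estimate non-linear functions of model parameters". Relative change is coded as 100*(p1/p0 - 1) overall and for Panel 1, as 100*(q1/q0 - 1) for Panel 2, and as the plain difference of the two between panels. The code is introduced with "code similar to the following may be used". Neither document mentions a log, logit or other transformed interval for these quantities.

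Attachment 1 checks precision at slope SDs of 0.5, 1.0 and 2.0 on the logit scale, because "In contrast, inter-subject differences in the slopes are unknown".

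**The concern.** ESTIMATE returns the estimate plus or minus t times a delta-method standard error. Relative reduction has a ceiling of 100%, and the true within-panel values in Table 10 run from 66.7% to 96.7%. With 8 to 12 participants per panel and a large slope SD, the estimated ratio p1/p0 is skewed, so symmetric limits sit in the wrong place. They reach too far towards 100% and not far enough towards smaller reductions.

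Relative change is one of two model-based scales for the primary endpoint. With no test planned, the interval is the main statement of uncertainty. A reader would take 80% limits to be wrong about equally often in each direction, and would expect every limit to be attainable.

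The SAP's simulation cannot show the problem. Table 11 gives limits averaged over 1000 simulations, reports no coverage, and omits within-panel relative-change intervals.

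**Working it through.** **Inputs.** From SAP Attachment 1: intercept SD 1.0; slope SD 0.5, 1.0 or 2.0; 8, 10 or 12 per panel; roughly 22,000 hepatocytes per biopsy (log N centred on 10); Scenario A 75% to 5% (Panel 1) and 30% to 1% (Panel 2); Scenario B 75% to 5% and 30% to 10%; Scenario C 60% to 20% and 30% to 10%. Attachment 1 expects 9-10 usable participants per panel after 20% dropout, so 9 was added. From Attachment 3: alpha 0.2. Symmetric limits using t on subjects minus 2 degrees of freedom are taken as NLMIXED's default behaviour; the SAP does not state this.

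**Reproducing the plan's figure.** Table 11, Scenario A, slope SD 2.0, 8 per panel, overall relative reduction: 95.1% (91.9, 98.4), width 6.5. Simulation with symmetric raw-scale limits gives 95.2% (92.0, 98.4), width 6.4. The stated limits lie 3.2 and 3.3 points from the estimate, as symmetric limits would.

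**Formula.** Let R = p1/p0. With biopsies this large, subject logits are almost exact, so with n per panel

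SE(log R) = sqrt{[(p0 - p1)² SD_int² + (1 - p1)² SD_slope²] / n}.

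The raw upper limit for the reduction is 1 - R + t × R × SE(log R). It exceeds 1 exactly when t × SE(log R) > 1.

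**Example at the true values: Scenario A, Panel 1, slope SD 2.0, n = 8.**
- SE(log R) = sqrt[(0.70² × 1 + 0.95² × 4)/8] = sqrt[(0.49 + 3.61)/8] = 0.716.
- t on 14 df is 1.345, so t × SE = 0.963.
- Raw limits: 93.3% ± 100 × 0.0667 × 0.963 = 93.3% ± 6.4, that is 86.9% to 99.8%.
- Log limits: 1 - 0.0667 × exp(±0.963), that is 82.5% to 97.5%.

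The product is close enough to 1 for sampling variation to carry some trials past it. At n = 12 it is 1.321 × sqrt(4.10/12) = 0.77. At slope SD 1.0 and n = 8 it is 1.345 × sqrt[(0.49 + 0.9025)/8] = 0.56.

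**Simulated raw intervals, Scenario A, within panel** (at least 20,000 trials per cell, nominal 10% per side):

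| Slope SD | n per panel | Limit past 100% | Overstates | Understates |
|---|---|---|---|---|
| 1.0 | 8-12 | none | 14-16% | 5-7% |
| 2.0 | 8 | 20-22% | 18-19% | 2-3% |
| 2.0 | 9 | 11-12% | 18% | 2-3% |
| 2.0 | 10 | about 5% | 17-18% | about 3% |
| 2.0 | 12 | under 1% | about 17% | 2-4% |

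Full Laplace maximum-likelihood fits to binomial counts (600 trials per cell, slope SD 2.0) agree: 19% pass 100% at n = 8 and 6-8% at n = 10, with limits up to 103.8%.

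**Other cells.** Across all scenarios, slope SDs and sample sizes, within-panel misses are heavier on the overstating side. At slope SD 0.5 in Scenario C and in Scenario B Panel 2 the split is only about 12% to 10%. No interval passes 100% at slope SD 0.5 or 1.0. The pooled overall interval passes 100% in at most 2.9% of trials.

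**Log-ratio intervals on the same data.** Within panel they miss about 9-11% overstating and 11-15% understating, and never pass 100%. For the between-panel difference in Scenario B, slope SD 2.0, n = 12, the raw interval lies wholly above the truth in 5.5% of trials and wholly below it in 16.7%. MOVER on the log-ratio limits gives 11.3% and 11.0%.

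**The case against.** Most of the case against this point concerns its scope, and it stands.

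- A reader might infer that impossible limits are a general feature of the planned analysis. They are not. They need the largest slope SD tried and few evaluable participants, and they almost vanish at the target of 12 per panel.
- A reader might infer that the 80% intervals under-cover and that a log interval restores coverage. Raw within-panel intervals cover about 74-80% in total, and log intervals about 75-79%. The pooled interval over-covers in most cells, up to 99% in Scenario B, because its model treats the panel difference as random variation. A log scale does not address that.
- The log interval leaves a smaller, reversed tilt in places. Scenario C, Panel 1, slope SD 2.0, n = 8 gives 9.8% overstating and about 15% understating.
- The code is illustrative, the study is exploratory, and no decision rule uses a limit. The sample-size text rests mainly on absolute change, and SAP 5.3.1.2.3 also describes the observed changes.

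None of this removes the one-sided error. It appears in every within-panel cell, including at slope SD 1.0, where no limit passes 100%.

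**Conclusion.** The point holds as a modest improvement to the analysis code, not as a threat to the study's validity. On the plan's own assumptions, the within-panel raw-scale intervals overstate the reduction in about 12-19% of trials and understate it in about 2-10%. The imbalance is marked in Scenario A at slope SD 1.0 to 2.0 and slight at SD 0.5 in Scenario C and Scenario B Panel 2. Overshoot matters if the true slope SD is near 2.0 and evaluable numbers fall to 8-10 per panel. The SAP calls the slope variability unknown and itself expects 9-10.

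The result rests on Attachment 1's data model with uncorrelated intercepts and slopes, on ESTIMATE's default limits, and on the SAP's target of the value for a participant with zero random effects.

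**What to change.** In Attachment 3:

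1. Add ESTIMATE statements for log(p1/p0), in the overall and the between-panel models, and for log(q1/q0). Report 100*(exp(limit) - 1) as the 80% limits for relative change.
2. For the between-panel difference, use MOVER. With reductions r1 and r2 and back-transformed limits (l1, u1) and (l2, u2), the lower limit is (r1 - r2) - sqrt[(r1 - l1)² + (u2 - r2)²] and the upper is (r1 - r2) + sqrt[(u1 - r1)² + (r2 - l2)²]. Convert these to the SAP's change scale by reversing the signs and swapping the limits.
3. If p0, p1, q0 and q1 are reported, which the SAP leaves optional, back-transform their logit limits so that they stay within 0-100%. In Scenario A at slope SD 2.0 and n = 8, the raw lower limit is negative in 29% of trials for p1 and 40% for q1.

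The cost is a few lines of code, one calculation outside ESTIMATE, and asymmetric intervals. Mean width for the ratio rises by 0-15%, most at slope SD 2.0 with 8 per panel (Scenario A: 14.2 to 16.1 points in Panel 1, 7.4 to 8.5 in Panel 2). In Scenario A with 12 per panel, the between-panel interval widens from 6.7 to 6.9 points at slope SD 1.0 and from 13.0 to 14.6 at 2.0. No extra data are needed.
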